8.6. Subject Study Diary

The site will provide each subject with a subject study diary on Day 1 prior to dosing. The date and time of study drug administration, the number of capsules taken, and confirmation that study drug was taken with breakfast and evening meal will be documented each day. The diary will be reviewed for completeness at the Day 7 visit. The subject will return the diary at the Day 14 visit.

8.7. Specific Study Period Information

8.7.1. Screening Period (Study Days -28 to -8)

After obtaining informed consent by the subject's parent(s) or legal guardian, and study subject assent, subjects will undergo screening procedures within 21 days of Day -7.

The following study evaluations and tasks will be performed during screening:

- Assess inclusion/exclusion criteria.
- Collect medical history.
- Perform a physical examination including height and weight.
- Collect vital signs.
- Perform 12-lead ECG in triplicate (1 to 3 minutes apart).
- Perform a serum pregnancy test (β-hCG) for female subjects of childbearing potential.
- Collect blood sample for serology testing (HIV-Ab, HBsAg, and HCV-Ab).
- Collect blood sample for clinical laboratory and parameters.
- Collect urine sample for urinalysis.
- Collect urine for drug screen (central laboratory) and perform alcohol breath test.

- Collect blood sample for PD biomarkers between 0700 and 1000 hours (prior to first morning dose of hydrocortisone). Subject must have serum 17-OHP level ≥800 ng/dL to be enrolled in the study.
- Administer the C-SSRS (Children's Screening/Baseline version).
- AE monitoring.
- Record prior and concomitant medications.

Eligible subjects will be instructed to return to the study center on Day -7.

8.7.2. Day -7 to Day -6: 24-Hour Baseline Pharmacodynamics

Subjects who continue to meet eligibility requirements will return to the study center for a 24-hour in-patient stay, during which blood samples will be collected for PD analysis. Subjects will not take their usual morning dose of steroidal treatment until after the 1000 hours PD sample is collected on Day -6.

The following study evaluations and tasks will be performed on Day -7 to Day -6:

- Update inclusion/exclusion criteria and medical history.
- Collect vital signs.
- Perform a urine pregnancy test (β -hCG) for female subjects of childbearing potential.
- Collect urine for drug screen and perform alcohol breath test. Urine testing kits will be provided by the central laboratory to confirm negative drug screen prior to PD collection. A separate urine sample will also be sent to the central laboratory for analysis.
- Collect blood samples for PD biomarkers at approximately 1845, 2000, 2300, 0100, 0300, 0700, 1000, 1500, and 1900 hours.
- AE monitoring.
- Record prior and concomitant medications.

Eligible subjects will be instructed to return to the study center on Day 1.

8.7.3. Treatment Period

The study will consist of a 14-day treatment period and will include 2 overnight in-patient stays (on Day 1 to Day 2 and Day 14 to Day 15) and a study center visit on Day 7.

8.7.3.1. Day 1 to Day 2

Subjects will be admitted to the study center on Day 1 and will be discharged in the evening of Day 2 after the 24-hour postdose procedures have been performed. Standard meals and snacks will be provided during the in-patient stay. The procedures to be conducted on these days are described in the following sections.

Day 1

Subjects will report to the study center on Day 1. The following study evaluations and tasks will be performed prior to dosing on Day 1:

- Update inclusion/exclusion criteria and medical history.
- Perform a physical examination including weight.
- Collect vital signs.
- Perform 12-lead ECG in triplicate (1 to 3 minutes apart).
- Perform a urine pregnancy test (β-hCG) for female subjects of childbearing potential.
- •
- Collect blood sample for clinical laboratory and parameters.
- Collect urine sample for urinalysis.
- Collect urine for drug screen and perform alcohol breath test. Urine testing kits will be provided by the central laboratory to confirm negative drug screen prior to dosing. A separate urine sample will also be sent to the central laboratory for analysis.
- Collect blood sample for PD biomarkers at 15 minutes predose (±5 minute window).
- Collect blood sample for PK at 15 minutes predose (±5 minute window).
- •
- Administer the C-SSRS (Children's Since Last Visit version).
- AE monitoring.
- Record prior and concomitant medications.
- Provide subject with a subject study diary and instruct him/her to document in the diary the date and time of study drug administration, the number of capsules taken, and confirmation that study drug was taken with breakfast and evening meal each day.

At approximately 1900 hours, each subject will receive study drug with the evening meal as described in Section 9.3.

The following study evaluations and tasks will be performed after dosing on Day 1 while the subject remains in bed (as applicable):

- Collect blood samples for PD biomarkers at 1, 4, and 6 hours postdose (±5 minute window).
- Collect blood samples for PK at 1, 4, and 6 hours postdose (±5 minute window).
- AE monitoring.
- Record concomitant medications.

Day 2

The subjects' usual morning dose of concurrent steroidal treatments, study drug dosing, and breakfast (snacks will be allowed prior to breakfast) will be delayed until after the 15 hour postdose PD samples are collected (ie, at approximately 1000 hours).

The following study evaluations and tasks will be performed on Day 2:

- Perform a physical examination.
- Collect vital signs between 8 and 10 and 22 and 24 hours post-evening dose (ie, morning and evening).
- Perform 12-lead ECG in triplicate (1 to 3 minutes apart) predose.
- Collect blood samples for PD biomarkers at 8, 12, 15, 20, and 24 hours post-evening dose (±15 minute window).
- Collect blood samples for PK at 8 and 12 hours post-evening dose (±15 minute window).
- •
- AE monitoring.
- Record concomitant medications.

The following procedures will be conducted *before* subjects may be discharged from the study center:

- At approximately 1900 hours, each subject will receive study drug with their evening meal as described in Section 9.3.
- Instruct male subjects and female subjects of childbearing potential who do not practice total abstinence to continue using contraception.
- Instruct subjects to notify the investigator or study staff by telephone if they experience any AEs and before taking any concomitant medications.
- Instruct subjects to continue taking study drug with breakfast (approximately 0700 hours) and with their evening meal (approximately 1900 hours) through Day 13 as described in Section 9.3, and to document in the diary the date and time of study drug administration, the number of capsules taken, and confirmation that study drug was taken with breakfast and the evening meal each day.
- Instruct subjects to bring the subject study diary as well as the remaining study drug back for the Day 7 visit.

Sites should call subjects between the Day 2 and Day 7 visits to remind them to complete the subject study diary, check on compliance, and remind them to bring subject study diary and remaining study drug to the Day 7 visit.

8.7.3.2. Day 7

The following procedures will be performed at the study center on Day 7:

- Perform a physical examination.
- Collect vital signs.
- Perform a urine pregnancy test (β-hCG) for female subjects of childbearing potential.
- Collect blood samples for PD biomarkers at approximately 12 hours (±2 hour window) after the Day 6 evening dose and prior to the Day 7 morning dose.
- Collect blood samples for PK at approximately 12 hours (±2 hour window) after the Day 6 evening dose and prior to the Day 7 morning dose.
- Check subject study diary.
- Study drug reconciliation.
- AE monitoring.
- Record concomitant medications.

The following additional procedures will be conducted on Day 7:

- Instruct subjects to perform study drug dosing (as described in Section 9.3) and subject study diary entry at home.
- Instruct subjects to return to the study center on Day 14 before evening dosing and to bring their study drug bottle including any unused study drug, and their subject study diary.

8.7.3.3. Day 14 to Day 15

Subjects will return to the study center on Day 14 and will be discharged in the evening of Day 15 after the 24-hour postdose procedures have been performed. Standard meals and snacks will be provided. The procedures to be conducted on these days are described in the following sections.

Day 14

Subjects will return to the study center on Day 14. The following study evaluations and tasks will be performed prior to evening dosing on Day 14:

- Collect vital signs.
- Perform 12-lead ECG in triplicate (1 to 3 minutes apart).
- Collect blood sample for PD biomarkers at 15 minutes predose (±5 minute window).
- Collect blood sample for PK at 15 minutes predose (±5 minute window).
- Collect urine for drug screen and perform alcohol breath test.
- Collect the study drug bottle including any unused study drug.

- Study drug reconciliation.
- AE monitoring.
- Record concomitant medications.

At approximately 1900 hours, each subject will receive study drug with their evening meal as described in Section 9.3. After study drug dosing, subjects will record in the subject study diary the date and time of study drug administration, the number of capsules taken, and confirmation that study drug was taken with the evening meal. The subject study diary will then be collected. Subjects will then go to bed.

The following procedures will be conducted after evening dosing on Day 14 while the subject remains in bed (as applicable):

- Collect blood samples for PD biomarkers at 1, 4, and 6 hours post-evening dose (±5 minute window).
- Collect blood samples for PK at 1, 4, and 6 hours post-evening dose (±5 minute window).
- AE monitoring.
- Record concomitant medications.

Day 15

The subjects' usual morning dose of concurrent steroidal treatments will be administered after the 15 hour postdose PD samples are collected (ie, at approximately 1000 hours) on Day 15.

The following procedures will be performed on Day 15:

- Perform a physical examination including weight.
- Collect vital signs between 8 and 10 and 22 and 24 hours post-evening dose (ie, morning and evening).
- Perform 12-lead ECG in triplicate (1 to 3 minutes apart).
- Perform a urine pregnancy test (β-hCG) for female subjects of childbearing potential.
- Collect blood sample for clinical laboratory and parameters.
- Collect urine sample for urinalysis.
- Collect blood samples for PD biomarkers at 8, 12, 15, 20, and 24 hours post-evening dose (±15 minute window).
- Collect blood samples for PK at 8, 12, and 24 hours post-evening dose (±15 minute window).
- •
- Administer the C-SSRS (Children's Since Last Visit version).
- AE monitoring.
- Record concomitant medications.

The following procedures will be conducted before subjects may be discharged from the study center:

- Instruct male subjects and female subjects of childbearing potential who do not practice total abstinence to continue using contraception.
- Instruct subjects to notify the investigator or study staff by telephone if they experience any AEs and before taking any concomitant medications.
- Confirm if the subject prefers to have the Days 17 and 21 visits conducted at home instead of at the study center.
 - If the subject elects to have a home visit, instruct him/her that the qualified home healthcare provider will contact him/her to schedule the visit.
 - If the subject elects to come into the study center, instruct him/her to return on Days 17 and 21.

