Subjects will be admitted to the study center on Days 1 and 14 (first and last day of dosing). Subjects will have a blood sample collected on Day 1 for the first dose of study drug. The first dose of study drug, NBI-74788 50 mg, will be administered at approximately 1900 hours with subjects' evening meal on Day 1. Study drug will be administered at the study center on Days 2 and 14 with subjects' breakfast and evening meals, respectively. The subjects' usual morning dose of concurrent steroidal treatments, study drug dosing, and breakfast (snacks will be allowed prior to breakfast) will be delayed until after the 15-hour postdose PD samples are collected (ie, at approximately 1000 hours) on Day 2. The subjects' usual morning dose of concurrent steroidal treatments will be administered after the 15-hour postdose PD samples are collected (ie, at approximately 1000 hours) on Day 15. Subjects will be discharged from the study center in the evening on Days 2 and 15 following completion of all study-related procedures for those days. Study drug will be self-administered at home under parent/guardian supervision at approximately 0700 hours (with breakfast) and 1900 hours (with evening meal) on Days 3 to 13.

On Day 7 during the treatment period, PK, PD, and safety assessments will be conducted in an outpatient setting at the study center.

Follow-up visits on Days 17 and 21 will be conducted at the study center or by a qualified home healthcare provider at the subject's home (based on the subject's preference). A final study visit will be conducted at the study center approximately 3 weeks after the last dose of study drug (on Day 35 or early termination). There will be a visit window of -8 hours for Day 7, -8 hours/+3 days for Days 17 and 21, and +7 days for the final study visit (Day 35 or early termination). Safety, tolerability, PK, and PD will be assessed at scheduled times throughout the study.

Study Population: Approximately 12 pediatric female and male subjects (14 to 17 years of age) with a documented medical diagnosis of classic 21-hydroxylase deficiency CAH, who meet all protocol eligibility criteria, will be enrolled.

Duration of treatment: The expected duration of study participation for each subject is approximately 9 weeks, including up to approximately 3 weeks for screening, a 24-hour PD baseline period (approximately 7 days prior to the first day of dosing), 14 days of dosing, and a follow-up period of approximately 3 weeks.

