Subjects will be admitted to the study center on Days 1 and 14 (first and last day of dosing). Subjects will have a blood sample collected on Day 1 for assessments will be collected on Day 1 prior to the first dose of study drug. The first dose of study drug, NBI-74788 50 mg, will be administered at approximately 1900 hours with subjects' evening meal on Day 1. Study drug will be administered at the study center on Days 2 and 14 with subjects' breakfast and evening meals, respectively. The subjects' usual morning dose of concurrent steroidal treatments, study drug dosing, and breakfast (snacks will be allowed prior to breakfast) will be delayed until after the 15-hour postdose PD samples are collected (ie, at approximately 1000 hours) on Day 2. The subjects' usual morning dose of concurrent steroidal treatments will be administered after the 15-hour postdose PD samples are collected (ie, at approximately 1000 hours) on Day 15. Subjects will be discharged from the study center in the evening on Days 2 and 15 following completion of all study-related procedures for those days. Study drug will be self-administered at home under parent/guardian supervision at approximately 0700 hours (with breakfast) and 1900 hours (with evening meal) on Days 3 to 13.

On Day 7 during the treatment period, PK, PD, and safety assessments will be conducted in an outpatient setting at the study center.

Follow-up visits on Days 17 and 21 will be conducted at the study center or by a qualified home healthcare provider at the subject's home (based on the subject's preference). A final study visit will be conducted at the study center approximately 3 weeks after the last dose of study drug (on Day 35 or early termination). There will be a visit window of -8 hours for Day 7, -8 hours/+3 days for Days 17 and 21, and +7 days for the final study visit (Day 35 or early termination). Safety, tolerability, PK, and PD will be assessed at scheduled times throughout the study.

The study design schematic is shown in Figure 1. A schematic of study drug dosing and blood draw timepoints is shown in Table 1.

Figure 1: Study Design Schematic

| | Screening | PD Baseline | 14-Day Dosing Period | | Follow-Period | | Final Study Visit/ET | | |
|-----|-----------|-------------|----------------------|--------------------------|---------------|-------|-------------------------|-----|----|
| | | | | | | | | | • |
| | | | | NBI-74788 (50 mg bid) | | | | | |
| | ı | 1 | ı ı | ı | 1 | 1 1 | ı | | 1 |

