| | | | | | | | | | |
| Day | -28 to -8 | -7 to -6 | 2 | 7 | 14 1 | 15 17 | 21 | 1 3 | 35 |

bid=twice daily; ET=early termination; PD=pharmacodynamic.

Table 1: Study Drug Dosing and Blood Draw Timepoints Schematic

| Screening | PD Baseline (Day -7) | PD Baseline (Day -6) | Day 1 | Day 2 | Day 3 - Day 6 | Day 7 | Day 8 - Day 13 | Day 14 | Day 15 | Day 17 | Day 21 | Day 35 |
|--|----------------------------------|----------------------------------|-----------------------------|---|---------------|-------------------|----------------------|------------------------------|--|----------------------|--------------------------|----------------------------|
| | | PD: 0100, 0300, 0700 hr | | PK/PD: 8, 12 hr post | | PK/PD: Predose | | | PK/PD: 8, 12 hr post | | | |
| AM DOSIN | G | | | 1000 hr Delayed Dosing with Meal | 0700 hr | 0700 hr | 0700 hr | 0700 hr | | | | |
| PD/Labs: 0700 – 1000 hr (+ & & Serology) | | PD: 1000, 1500, 1900 hr | PK/PD/Labs: Predose + | PD: 15, 20, 24 hr post | | | | PK/PD: Predose | PD: 15, 20 hr post PK/PD/Labs: 24 hr post | PK: 72 hr post | PK/PD: 168 hr post | PK/Labs: 504 hr post |
| PM DOSIN | G | | 1900 hr | 1900 hr | 1900 hr | 1900 hr | 1900 hr | 1900 hr | | | | |
| | PD: 1845, 2000, 2300 hr | | PK/PD: 1, 4, 6 hr post | | | | | PK/PD: 1, 4, 6 hr post | | | | |

PD=pharmacodynamic; PK=pharmacokinetic.

Note: blood draws (pre- and post-dose) are relative to evening dosing.

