9.3. Study Drug Administration

Subjects will take a study drug capsule by mouth starting at approximately 1900 hours beginning on Day 1, and then at approximately 0700 hours and 1900 hours for 14 consecutive days. Study drug will be administered at the study center on Days 2 and 14 with subjects' breakfast and evening meals, respectively, and on Day 1 with subjects' evening meal. The subjects' usual morning dose of concurrent steroidal treatments, study drug dosing, and breakfast (snacks will be allowed prior to breakfast) will be delayed until after the 15 hour postdose PD samples are collected (ie, at approximately 1000 hours) on Day 2.

Each dose of study drug is to be administered a meal (breakfast or the evening meal); each meal should be completed within administration. The date and time of study drug administration, the number of capsules taken, and confirmation that study drug was taken with breakfast and the evening meal will be documented each day.

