4. STUDY DESIGN

4.1. Summary of Study Design

This is a Phase 2, open-label, multiple-dose study to assess the safety, tolerability, PK, and PD of crinecerfont in approximately 12 pediatric female and male subjects (14 to 17 years of age) with a documented medical diagnosis of classic 21-hydroxylase deficiency CAH. Crinecerfont 50 mg bid will be administered for 14 consecutive days with breakfast and evening meals beginning on the evening of Day 1.

[figure not shown]
Eligible subjects who have a screening 17-OHP level ≥800 ng/dL will be admitted to the study center on Day -7 for 1 night and have baseline serial PD samples collected over a 24-hour period beginning that evening. Baseline serial PD samples will be collected at approximately 1845, 2000, 2300, 0100, 0300, 0700, 1000, 1500, and 1900 hours.

The subjects' usual morning dose of steroidal treatments will be administered after the 1000 hours PD sample is collected on Day -6. Subjects will be discharged on Day -6 after the last PD sample is collected.

Subjects will be admitted to the study center on Days 1 and 14 (first and last day of dosing). The first dose of study drug, crinecerfont 50 mg, will be administered at approximately 1900 hours with subjects' evening meal on Day 1. Study drug will be administered at the study center on Days 2 and 14 with subjects' breakfast and evening meals, respectively. The subjects' usual morning dose of concurrent steroidal treatments, study drug dosing, and breakfast (snacks will be allowed prior to breakfast) will be delayed until after the 15-hour postdose PD samples are collected (ie, at approximately 1000 hours) on Day 2. The subjects' usual morning dose of concurrent steroidal treatments will be administered after the 15-hour postdose PD samples are collected (ie, at approximately 1000 hours) on Day 15. Study drug will be self-administered at home under parent/guardian supervision at approximately 0700 hours (with breakfast) and 1900 hours (with evening meal) on Days 3 to 13.

The study design schematic is shown in Figure 1.

Figure 1: Study Design Schematic

bid=twice daily; ET=early termination; PD=pharmacodynamic; NBI-74788=crinecerfont.

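### The discharge and home-dosing text stops at Day 13, but Table 1 schedules a 0700 dose on Day 14; following the text would double the gap before the only multiple-dose serial PK profile

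*Protocol*

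**What the plan says.** Five places end home dosing on Day 13:

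- Protocol 8.7.3.1, Day 2 discharge, where the instruction for subjects reads: "continue taking study drug with breakfast (approximately 0700 hours) and with their evening meal (approximately 1900 hours) through Day 13 as described in Section 9.3".
- Protocol synopsis: self-administration at 0700 "hours (with breakfast) and 1900 hours (with evening meal) on Days 3 to 13".
- Protocol Section 6: "1900 hours (with evening meal) on Days 3 to 13".
- Protocol Table 2, dosing footnote: the same sentence.
- SAP 4.1: "with evening meal) on Days 3 to 13".

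The accompanying text on dosing at the center pairs Day 2 with breakfast and Day 14 with the evening meal. No morning dose is given at the center on Day 14.

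Three places point to a Day 14 morning dose:

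- Protocol Table 1, AM dosing row, from Day 2 onward: "1000 hr Delayed Dosing with Meal | 0700 hr | 0700 hr | 0700 hr | 0700 hr". Against the column headers, the four 0700 entries belong to Days 3-6, Day 7, Days 8-13 and Day 14.
- Protocol 9.3: an evening dose on Day 1, "then at approximately 0700 hours and 1900 hours for 14 consecutive days".
- Protocol 8.7.3.2 (Day 7): subjects are to dose as in Section 9.3, and the site is to "Instruct subjects to return to the study center on Day 14 before evening dosing".

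In Protocol 8.7.3.3, the Day 14 tasks before the evening dose include collecting the bottle and reconciling study drug, but not reviewing the diary. The diary is completed for the evening dose, and only then: "The subject study diary will then be collected".

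**The concern.** Table 1 is the only place that gives the Day 14 morning dose by day and time. The text that sites act on assigns it neither to the home nor to the center, and the discharge instruction sets an end date before it.

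The Day 14 to 15 profile is the only serial PK profile after repeated dosing. It is the sole source of Cavg, %fluctuation, the accumulation ratio and CL/F, and it supplies the multiple-dose AUC0-12 and Cmax. If the 0700 dose is left out, these values no longer describe 12-hourly dosing.

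The PD results are exposed too. The morning window in SAP 9.2 is 12 and 15 h after the evening dose, when drug levels would also be lower. Those Day 14 values feed the responder summaries in SAP 9.3 and are plotted against AUC0-12 and Cmax in SAP 9.4. An omission would show up later in the recorded dose times, but the profile could not be repeated.

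**Working it through.** **Dose count**

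| Source | Doses added | Total |
|---|---|---|
| Summary narrative (synopsis, Section 6, SAP 4.1) | Day 1 evening 1 + Day 2 breakfast 1 + Days 3-13 (11 × 2 = 22) + Day 14 evening 1 | 25 |
| Protocol 8.7.3.1 | Day 2 evening, 1 | 26 |
| Protocol Table 1 | Day 14 at 0700, 1 | 27 |

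**Interval before the Day 14 profile dose (1900)**

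- Table 1 followed: 0700 to 1900 on Day 14 = 12 h, or 11.75 h to the predose sample.
- Day 13 wording followed: Day 13 1900 to Day 14 1900 = 24 h, or 23.75 h to the predose sample.

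**Size for one affected subject**

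The documents give neither a half-life nor an absorption rate, and the visible text gives no formula for CL/F or the accumulation ratio. The following are therefore assumptions:

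- One-compartment oral model. The concentration at time t is the sum over doses given at times s ≤ t of [ka/(ka − k)]·[exp(−k(t − s)) − exp(−ka(t − s))], up to a constant, with k = ln 2/half-life.
- Dose times from Table 1, with 0 h = Day 1 1900: 0, 15 (the delayed 1000 dose), 24, then every 12 h to 312. The omitted dose is the one at 300 h.
- AUC and Cmax taken over 312-324 h; CL/F = dose/AUC0-12; accumulation ratio = Day 14 AUC0-12 / Day 1 AUC0-12; predose level at 311.75 h; morning window at 324 and 327 h.

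Results at ka 0.7/h, without the 300 h dose compared with all 27 doses:

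| Half-life (h) | 4 | 6 | 12 | 24 | 48 | 72 |
|---|---|---|---|---|---|---|
| AUC0-12 lower by (%) | 14.5 | 22.5 | 27.2 | 21.6 | 13.8 | 10.3 |
| Cmax lower by (%) | 14.3 | 22.0 | 26.9 | 21.5 | 13.8 | 10.3 |
| CL/F higher by (%) | 17.0 | 29.0 | 37.5 | 27.6 | 16.0 | 11.5 |
| Predose level lower by (%) | 87.5 | 75.0 | 50.0 | 29.3 | 16.1 | 11.5 |
| Accumulation ratio, 27 doses | 1.20 | 1.43 | 2.20 | 3.81 | 7.01 | 9.88 |
| Accumulation ratio, dose omitted | 1.02 | 1.11 | 1.60 | 2.99 | 6.04 | 8.86 |
| Morning-window drug level lower by (%) | 11 | 19 | 25 | 21 | 14 | 10 |

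The CL/F row follows from the AUC row: at 4 h, 1/(1 − 0.145) − 1 = 17.0%.

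Over the same half-lives, the AUC0-12 loss is 10-25% with instantaneous absorption, 10-26% at ka 1.5/h and 10-30% at ka 0.3/h.

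Closed-form check: with instantaneous absorption at steady state, the fraction of AUC0-12 lost is r(1 − r), where r = exp(−12k). At a 12 h half-life r = 0.5, giving 0.5 × 0.5 = 25%. At 4 h r = 0.125, giving 0.125 × 0.875 = 10.9%.

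**The case against.** The strongest reply is that this is an omission and the intended regimen is clear. No sentence says there is no Day 14 morning dose. The narrative also leaves out the Day 2 evening dose, so it was never a full dose list, and four of the five places repeat one summary sentence. The discharge instruction cites Section 9.3, and the Day 7 instruction cites it again with no Day 13 limit. The diary and other material handed to subjects are not among the documents, so what subjects read is unknown.

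Much of this stands. The four narrative sentences alone are omissions, and a careful site would probably infer the dose. But the discharge instruction sets its own end date, and neither Section 9.3 nor the Day 7 text names the Day 14 0700 dose.

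A second reply is that safeguards exist: capsule reconciliation on Day 14, dose times on the eCRF and in the diary (Protocol 9.6), and the missed-dosing exclusion in SAP 10.1. They help, but only in part. A capsule count cannot date a miss, and the expected total is 26 or 27 depending on which text is used. The exclusion sits with the concentration summaries, and the visible text of SAP 10.2 does not extend it to the PK parameters. A subject who stopped as instructed might also not be classed as deviating.

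A third reply concerns the size. The lower bound of about 10% depends on the half-life range: r(1 − r) gives 5.9% at 3 h and 1.5% at 2 h. PK sampling runs to 504 h, and if a long terminal phase carries little of the AUC, the loss could be smaller than a one-compartment model shows. These limits are real.

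**Conclusion.** The concern holds as a wording inconsistency in an operational dosing instruction. The 24 h against 12 h interval and the 26 against 27 doses follow from the documents without any assumption. The PK effect is per affected subject and rests on the assumed model: about 10% to 30% lower Day 14 AUC0-12 for half-lives of 4 to 72 h across the absorption rates tried, and less for half-lives under 4 h. The effect on the biomarkers cannot be computed from the documents. The number of subjects affected is unknown and may be zero, and no group-level effect is claimed. With about 12 subjects planned, each lost profile would be about 1/12 = 8% of the multiple-dose PK data. The plan should be corrected, but nothing in the design itself needs to change.

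**What to change.** - In the synopsis, Section 6, the Table 2 dosing footnote and SAP 4.1, extend home dosing to *Days 3 to 13 and the morning of Day 14*.
- In Protocol 8.7.3.1, change the end of the discharge instruction to *through the morning of Day 14*.
- In Protocol 8.7.3.3, add a check of the Day 14 0700 dose time from the diary before the predose sample.
- If that dose was not taken, apply the SAP 10.1 missed-dosing exclusion to that subject's Day 14 PK parameters, and say so in SAP 10.2.

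The cost is five wording corrections, one added check and one clarifying sentence in the SAP. Subjects already bring the diary on Day 14 and dose times are already recorded, so no new visit, sample or data field is needed.
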